6.3.6 End of Study and Follow-up

Withdrawal/End of Treatment (Visit 7)

This hybrid visit will be conducted for subjects who have completed their treatment at Visit 7, subjects who wish early withdrawal or subjects whom the investigator deems participation is no longer effective or safe.

Participants will return to the study site for Visit 7 within 7 days of Visit 6. The following procedures and assessments will be performed at Visit 7: vital signs, AISRS, CGI-S, WebNeuro battery assessments (Verbal Interference/Stroop,Go/No-Go,CPT/TOVA), TASS, Expanded ASRS, C-SSRS and BRIEF-A.

Concomitant medications and AEs, if any, will be noted and drug accountability and compliance will be performed. Participants should report taking at least 80% of the prescribed study medication in order to be considered compliant.

The TASS will be done three times this day. The recommended dosing is at 5 am +/- 1 hour. The first TASS is done at half hour to one hour post dose (5:30 to 6 am +/- 1 hour), the second TASS is done 4 hours post dose (9am +/- 1 hour) and the third TASS is done 14-15 hours post dose (7pm+/- 1 hour).

Once all assessments and procedures for this visit are completed, participants will be given the Adult ADHD Referral list to help with the transitioning into treatment as usual.

Those that complete the study, and at the principal investigator's discretion, as a curtesy, can request and receive a letter stating their diagnosis and participation in the study.

6.3.7 Removal of subjects

Early Withdrawal of Subjects

Patients can withdraw or take back their permission to use and share his/her health information at any time. When the patient withdraws their permission, they will not be able to take back information that has already been used or shared with others. In order to withdraw their permission from the study, patients must send a written notice to the principal investigator for the study noted on page one of their consent form. If patient withdraws their permission, he/she will not be able to stay in this study.

Patients will be withdrawn if, in the opinion of the study doctor, it is no longer safe for the patient to participate in the study. We can get verbal permission to follow-up with the patient in the event they suffer adverse events. We will document three attempts to contact the patient via phone. If unable to contact, we will send the patient a certified letter. (Attachment)

6.4 Statistical Method

6.4.1 Statistical Design

Statistical Analysis Plan: Our primary outcomes are the correlations of TASS ratings with AISRS ratings to examine overall ADHD ratings vs. ADHD ratings throughout the day into early evening. In secondary analyses, we will also analyze the following variables: Evaluation of ADHD symptoms on AISRS; the TASS 1 hour, 4 hours and 14-15 hours post dose: (total, inattentive and hyperactive-impulsive subsets); expanded ASRS (total, inattentive and hyperactive-impulsive, executive function and emotional control subsets); symptoms of executive function (BRIEF-A: GEC, metacognition, behavioral regulation scales and subscales: Inhibit, Shift, Emotional Control, Initiate, Working Memory, Plan/Organize, Organization of Materials, Monitor); and neuropsychological tests (Verbal Interference/Stroop: Color, Word and Interference Score;Go/No-Go: Accuracy, False Negative errors, False Positive errors, and Response Time; CPT/TOVA: Response Time Variability [RVP], Response Time, d', Errors of Omission, Errors of Commission, Post-Commission Response Times, Multiple Responses, Anticipatory Responses).

Our statistical analysis framework will be the general linear regression model. We will choose the distributional family and link function based on the distribution of the outcome variables. Each regression model will predict the outcome as the dependent variable with weeks in trial after the end of the single-blind placebo lead-in as the independent variable.

All analyses will use the ITT sample. For our design, a significant effect of week assesses the significance of the drug effect. We have chosen an IIT analyses as we can include all patients except for placebo responders in the analyses. We have chosen a single-blind placebo lead-in to define placebo responders, which are defined as patients who experience \geq 30% decrease in their total AISRS scores during placebo lead-in treatment and will be discontinued from the protocol. We anticipate that based on the literature that 10% or fewer of patients will be placebo responders and that the overall discontinuation rate in the trial will be 20% (*Manor et al. 2012*). Changes within the day in TASS ratings 1 hour post dose vs. 4 hours post dose vs. 14-15 hours post dose will also be analyzed via the general linear regression model. Correlations between ADHD and executive function ratings will be examined via Spearman's correlation coefficients.

Statistical Power Analysis

Justification for sample size: Up to 50 patients will be enrolled to be sure that 32 evaluable patients reach the end of treatment at week six. The graph shows power at different values of the Cohen's d effect size for estimating the difference between baseline and endpoint values. For our primary analysis, which uses a two-sided test with a type I error of 0.05, it shows that 32 evaluable patients will give power of 90% or more for effect sizes of 0.6 or greater. 0.6 is a reasonable expectation for an effect size; it is half of the 1.2 effect size reported by *Spencer et al.* (2008) REF and thus is at the lower end of what we should expect to see in this study.

6.4.2 Sample Size Considerations

Justification for sample size: Up to 50 patients will be enrolled to be sure that 32-30 evaluable patients reach the end of treatment at week six. The graph shows power at different values of the Cohen's d effect size for estimating the difference between baseline and endpoint values. Our primary analysis, which uses a two-sided test with a type I error of 0.05, shows that 32 evaluable patients will give power of 90% or more for effect sizes of 0.6 or greater. 0.6 is a reasonable expectation for an effect size; it is half of the 1.2 effect size reported by *Spencer et al.* (2008) and thus is at the lower end of what we should expect to see in this study.

6.4.3 Planned Analyses

6.4.3.1 Primary Analyses

Our statistical analysis framework will be the general linear regression model. We will choose the distributional family and link function based on the distribution of the outcome variables. Each regression model will predict the outcome as the dependent variable with weeks in trial after the end of the single-blind placebo lead-in as the independent variable. All analyses will use the ITT sample. For our design, a significant effect of week assesses the significance of the drug effect. We have chosen an IIT analyses as we can include all patients except for placebo responders in the analyses. We have chosen a single-blind placebo lead-in to define placebo responders, which are defined as patients who experience \geq 30% decrease in their total AISRS scores during placebo lead-in treatment and will be discontinued from the protocol. We anticipate that, based on the literature, 10% or fewer of patients will be placebo responders and that the overall discontinuation rate in the trial will be 20% (*Manor et al. 2012*). The changes within the day in TASS ratings, 1-hour post dose vs. 4 hours post dose vs. 14-15 hours post dose will also be analyzed via the general linear regression model. Correlations between ADHD and executive function ratings will be examined via Spearman's correlation coefficients.

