5.3 Study Population

The study population will consist of males and females between the ages of 18-55, inclusive. They will be referred from area clinicians, NYU clinicians via EPIC (slicer dicer) and advertisements such as flyers, online search engine searches and StudyKIK.

The population must have ADHD and no comorbid psychiatric issues requiring treatment; exception for major depression, dysthymia and anxiety disorders in remission, but stable on psychiatric medications for three weeks or more at the discretion of the principal investigator

They should also meet all inclusion and not meet any of the exclusion criteria. In the opinion of the investigator, subjects must be of good health and a good candidate for a clinical research trial.

Up to 50 patients will sign consent and be screened, 34 will be enrolled into the singleblind placebo lead-in, and 32 patients will be randomized into the four-week treatment phase to be sure that at least 30-32 evaluable patients reach the end of treatment at week six.

Good clinical practices will ensure we call subjects one week after their last dose of study medication to ensure they are not experiencing any adverse events and have connected to treatment as usual in the community.

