6.4.5 Handling of Missing Data

Missing outcome data will be handled in regards to analysis in the following way: last observation will be carried forward.

7 - Trial Administration

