7.14 Study Discontinuation

Stopping Rules

If subjects are experiencing a decline of 30% per the clinical assessments conducted, they will be withdrawn. Patient experiencing adverse events that, in the opinion of the investigator, the subject can no longer participate due to a change in medical status, experiences from adverse events, or patient becomes pregnant), the subject will be discontinued from the study. These are the possible reasons for termination from the study:

- Adverse events
- Lack of efficacy
- Lost to follow-up
- Pregnancy
- Withdrawal by subject
- Noncompliance
- Protocol violation
- Other

Documentation of study discontinuation will be added to subject source records. Withdrawal assessments will be conducted if investigator deems it is necessary. This will also be documented in the subject's source document folder..

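### The drug effect is the week coefficient from a regression of repeated AISRS scores with no subject term, so the 5% level is not assured, and unrestricted LOCF can count a placebo score as a Mydayis score

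*Combined protocol and SAP*

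**What the plan says.** Section 6.4.3.1 sets the primary model: "Each regression model will predict the outcome as the dependent variable with weeks in trial after the end of the single-blind placebo lead-in". Week is the only regressor named. The section adds that "a significant effect of week assesses the significance of the drug effect". Sections 5.1, 6.4.1 and 6.4.4 repeat this. The distributional family and link are to be chosen from the data. No subject effect, within-subject covariance, GEE or robust variance is named.

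By the schedule in the Synopsis, the AISRS is scored at every visit. Visit 3 gives the last placebo score and Visits 4 to 7 give the Mydayis scores. WebNeuro and BRIEF-A are done only at screening, Visit 3 and Visit 7.

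The analysis set is ITT because "we can include all patients except for placebo responders in the analyses"; no on-treatment score is required. The whole missing-data rule in 6.4.5 is that the "last observation will be carried forward".

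The power statement in 6.4.1 and 6.4.2 is for "estimating the difference between baseline and endpoint values": 32 evaluable patients, d = 0.6, two-sided 5%, power at least 90%.

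On early leavers, 6.3.6 says of the Visit 7 assessments: "This hybrid visit will be conducted for subjects who have completed their treatment at Visit 7, subjects who wish early withdrawal". Section 7.14 says: "Withdrawal assessments will be conducted if investigator deems it is necessary".

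The Appendices list a separate statistical analysis plan (Appendix 17) that is not in the supplied text. What follows concerns the supplied text only.

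**The concern.** In this single-arm, fixed-order design the week test carries the whole efficacy inference. Scores from one patient are correlated. A regression that treats up to 160 scores (32 × 5) as independent uses the wrong standard error for the week coefficient. The error can go either way, depending on a correlation the documents do not give. The text also does not settle whether Visit 3 (week 0) is a row in the model, although a post-lead-in week count allows either reading. The stated power belongs to a different test.

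Separately, LOCF without a treatment-phase limit, combined with this ITT set, puts a Visit 3 placebo score into the Mydayis weeks for anyone who starts Mydayis but is not scored again. For WebNeuro and BRIEF-A, which have no on-drug assessment before Visit 7, a missing Visit 7 becomes a change of exactly zero.

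Section 6.4.1 also names TASS–AISRS correlations as primary, while 5.1 and 6.4.4 name the AISRS total. Outcome, model rows and error structure are therefore all open to choice at analysis.

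**Working it through.** **1. The plan's own figure.** Paired t-test on change: noncentrality = 0.6 × √32 = 3.39 on 31 df, two-sided 5%, gives power 90.8%. With n = 30 it is 88.8%. The stated 90% therefore reproduces as a paired baseline-to-endpoint test, with d in units of the SD of change.

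**2. Level of the week regression.** Assumptions: 32 complete patients, unit variance at each visit, linear improvement, correlation 0.3, 0.5 or 0.7 under compound symmetry (CS) or AR(1). For weeks 0 to 4, the sum of squares of week is 10, so the regression takes SE(slope) = √(1/(32 × 10)) = 0.0559. The true variance is this variance times a factor v. Under CS, v = 1 − ρ. Approximate true level = 2 × [1 − Φ(1.96/√v)].
- CS 0.5: v = 0.5, 1.96/0.707 = 2.77, level 0.6%.
- AR(1) 0.5: v = 1.2, 1.96/1.095 = 1.79, level 7.4%.

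**3. Power of the week regression at paired d = 0.6.** Total change = 0.6 × SD of change; under CS, SD of change = √(2(1 − ρ)). Power ≈ Φ[(slope/SE − 1.96)/√v].
- CS 0.5, weeks 0–4: slope = 0.6 × 1.0/4 = 0.15; 0.15/0.0559 = 2.68; (2.68 − 1.96)/0.707 = 1.02; power about 85%.
- CS 0.7, weeks 0–4: slope = 0.6 × 0.775/4 = 0.116; 0.116/0.0559 = 2.08; (2.08 − 1.96)/0.548 = 0.22; power about 59%.
- CS 0.5, weeks 1–4: sum of squares 5, SE = √(1/160) = 0.0791; 0.15/0.0791 = 1.90; (1.90 − 1.96)/0.707 = −0.09; power about 46%.

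Simulation (40,000 runs), for correlation 0.3 / 0.5 / 0.7:

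| Rows in model | Structure | True level | Power |
|---|---|---|---|
| Weeks 0–4 | CS | 2.1% / 0.7% / 0.07% | 92% / 84% / 59% |
| Weeks 0–4 | AR(1) | 7.3% / 7.4% / 5.2% | 95% / 94% / 91% |
| Weeks 1–4 | CS | 2.0% / 0.7% / 0.06% | 63% / 46% / 20% |
| Weeks 1–4 | AR(1) | 5.9% / 5.1% / 2.6% | 75% / 73% / 66% |

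At CS 0.7 with weeks 0–4, power rises to 98% at d = 0.9 and about 100% at d = 1.2.

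**4. Subject-level tests on the same data.** Paired t: level 4.8–5.1%, power 90.8%. t-test on patient slopes: level 4.8–5.2%, power 90–96%. Subject effects with independent residuals (the random-intercept type) hold 5% under CS but give 10.0% / 13.7% / 17.3% under AR(1).

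**5. LOCF.** Assume a fraction q of Mydayis starters drop out, with last scores spread evenly over weeks 0, 1, 2 and 3, and linear improvement. The four groups lose 1, 0.75, 0.5 and 0.25 of their change, so the mean loss is (2.5/4)q = 0.625q. The week-0 group, where a placebo score is carried, accounts for q/4 = 0.25q; ordinary on-treatment carry-forward accounts for 0.375q.

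| q | Source | Placebo carried | Other LOCF | Patients of 32 with no Mydayis score (32q/4) |
|---|---|---|---|---|
| 6% | 2/32, from 30 of 32 finishing (5.3) | 1.6% | 2.3% | 0.5 |
| 11% | 1 − 0.80/0.90 (6.4.3.1: 20% overall, 10% placebo responders) | 2.8% | 4.2% | 0.9 |
| 20% | all 20% on Mydayis | 5.0% | 7.5% | 1.6 |

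The 6% row uses 5.3: "32 patients will be randomized into the four-week treatment phase to be sure that at least 30-32 evaluable patients reach the end of treatment". WebNeuro and BRIEF-A lose at most q (6%, 11% or 20%), and only if no early-withdrawal battery is obtained.

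**The case against.** The strongest reply is that 6.4.3.1 names a framework and does not fully specify a model. It neither states independence nor excludes a subject term, and Appendix 17 may supply one. That is why the claim is confined to the supplied text. But choosing a family and link does not model within-patient correlation, and no supplied section does.

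Second, the hypothesis in 4.1 measures improvement from the end of the lead-in, and the power contrast starts at baseline. Both favour including week 0. This stands as the more natural reading, so the weeks 1–4 power figures show what the ambiguity could cost and are not the expected case.

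Third, the 59% depends on scaling d by the SD of change. If 0.6 is in score-SD units, week-regression power (weeks 0–4) under CS is 80% / 84% / 90%. Under AR(1) it is 74–77%, against 65–76% for the paired test, so the regression is no worse there. At 1.2 score SDs, power is at least 99.9% in every setting. This is a fair sensitivity. The paired scaling is kept because it reproduces the stated 90%.

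Fourth, inflation is small (at most 7.4%), and LOCF dilutes the effect and does not create false positives. Both are correct, and the conclusion does not claim otherwise. Section 6.3.6 does plan the full battery at early withdrawal, but 7.14 makes it discretionary, so a final on-drug score is not guaranteed.

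**Conclusion.** The point holds for the supplied text. Fitted as written, the primary test has a level and power that depend on an unstated correlation and on whether week 0 is included. Most settings are conservative and lose power; some are mildly liberal; AR(1) at 0.7 with weeks 0–4 is close to 5%. The stated 90% power is sound for a paired change but does not describe this test. The sample size is not the problem.

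The LOCF effect on AISRS is modest and toward no effect: 3.9% to 12.5% of the change in total, of which 1.6% to 5.0% comes from placebo scores. Copied scores are also treated as observed.

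These sizes rest on assumed correlations, linear improvement, paired scaling of d and evenly spread dropout. The documents give none of these directly. It should be fixed before analysis; confidence is medium because of the unknown correlation and the unseen appendix.

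**What to change.** - **6.4.3.1:** name one primary analysis. Use a repeated-measures mixed model on all observed AISRS totals at Visits 3 to 7, with Visit 3 as baseline, categorical visit, unstructured within-subject covariance and small-sample degrees of freedom (for example Kenward–Roger). The primary contrast is Visit 7 minus Visit 3, matching 6.4.2. Name a single fallback for non-convergence: the paired Visit 7 minus Visit 3 test fits the powered contrast. A patient-slope t-test also holds its level but tests a different quantity. Avoid a random-intercept-only model.
- **Other repeated outcomes:** state a subject-level structure, including visit and time of day within patient for TASS.
- **6.4.5:** keep LOCF only as a sensitivity analysis in which a value from Visit 3 or earlier does not count as an observed Mydayis score, and report how many patients then lack an endpoint.
- **Reconcile** 6.3.6 with 7.14 on assessments at early withdrawal, and 6.4.1 with 5.1 and 6.4.4 on the primary outcome.

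Cost: wording and some programming. The mixed model relies on missing at random, which is open to question when adverse events and lack of efficacy are listed reasons for leaving (7.14). In simulation (6,000 runs, 11–20% dropout, t reference on completers minus 1) its level was 4.9–5.7%, its power at d = 0.6 was about 85–89%, and its estimate was 99–100% of the true change. A normal reference gave a level of 6.0–7.1%, hence the small-sample correction; Kenward–Roger itself was not simulated.

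The LOCF restriction leaves about 0.9 (q = 11%) or 1.6 (q = 20%) of 32 patients without an endpoint. The share of the true change retained becomes (1 − 0.625q)/(1 − 0.25q), rising from 93% to 96% or from 87.5% to 92% even when dropout is unrelated to outcome. It could rise further if early leavers do badly.

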4.1 Hypothesis

In subjects with adult ADHD after Mydayis treatment (from end of single-blind placebo lead-in) there will be significant improvement in:

1) Overall symptoms of adult ADHD as measured by the total score on the Adult ADHD Investigator Symptom Rating Scale (AISRS) (primary effect).

2) Overall inattentive (IA) and hyperactive-impulsive (HI) ADHD symptom subsets on the AISRS and overall impairment via the Clinical Global Impression-Severity (CGI-S) scale.

3) Total ADHD symptoms fourteen hours after AM dosing as measured via total scores on the Time Sensitive Adult ADHD Symptom Scale (TASS); Inattentive (IA) and hyperactive-impulsive (HI) ADHD symptom subsets (TASS) subsets.

4) In neuropsychological measurement of Executive Function in the early evening (fourteen to fifteen hours after morning dosing) as measured by (WebNeuro: Verbal Interference/Stroop, Go/No-Go, CPT/TOVA)

5) In clinical symptoms of Executive Function in the early evening, as measured by the BRIEF-A.

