5.1 General Design Description

Description of Study type

This will be a phase three, single-blind study, with a two-week, placebo lead-in and then a four-week forced titration treatment with Mydayis with starting dose of 12.5 mg/day with titration based on clinical response and potential adverse events.

Number and Description of Each Treatment Arm/Group

This will be a six-week trial after the screening period. After a two-week, subject singleblind, placebo lead-in, all patients will receive four weeks of Mydayis (12.5mg-37.5mg/day), with treatment order fixed. Study visits are hybrid; conducted remotely and in clinic.

Doses per Subject per Treatment

During the two-week, placebo lead-in, all subjects will receive 12.5mg Placebo at Visit 1 and Visit 2. During Visit 3, Mydayis treatment will be initiated at a dose of 12.5mg/day and will increase in increments of 12.5mg, based upon clinical response and tolerability, up to 25mg at Visit 4, up 37.5mg at Visit 5 and holding at the dose from visit 5 of up to 37.5mg at Visit 6. There will be no dispensation at Visit 7, which is the last in clinic/remote visit for this study. Patients will be seen weekly throughout the trial both in clinic and remote.

Our primary outcome is effects of Mydayis on overall adult ADHD symptoms via total AISRS Score. In secondary analyses, we will also analyze the following variables: Evaluation of ADHD subset IA and HI symptoms on the AISRS; TASS scores 1 hour, 4 hours and 14-15 hours post dose (total, inattentive and hyperactive-impulsive subsets) (for effects of Mydayis over time at different points of the day and within the day); expanded Adult ADHD Self Report Symptom Rating Scale (expanded-ASRS) Symptom Checklist (total, inattentive and hyperactive-impulsive, executive function and emotional control subsets); symptoms of executive function (BRIEF-A: GEC, metacognition, behavioral regulation scales and subscales: Inhibit, Shift, Emotional Control, Initiate, Working Memory, Plan/Organize, Organization of Materials, Monitor); and neuropsychological tests (WebNeuro: Verbal Interference/Stroop, Go/No-Go, CPT/TOVA): Response Time Variability [RVP], Response Time, d', Errors of Omission, Errors of Commission, Post-Commission Response Times, Multiple Responses, Anticipatory Responses).

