6.1.3 Method of Assignment/Randomization

There is no plan for an assignment/randomization method after screening is complete and principal investigator has evaluated subject to be eligible for the study. The pharmacy

will receive an electronic copy of the first and last page of the subject's signed inform consent with the subject's contact information sheet. The pharmacy will dispense to subjects on a weekly basis. The first two dispensations will be 12.5 mg placebo and the following four weeks will be Mydayis starting at 12.5 titrating up to 25mg then holding at 35.7 mg for two weeks.

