6.1.4 Blinding and Procedures for Unblinding

The study trial in regards to study drug is single blinded. The research staff, including study doctor, will know if the patient is receiving Mydayis or placebo. The subject will not know when they are on placebo or when they start the Mydayis treatment. The study pharmacist will know which study medication, either Mydayis or placebo, the patient is taking and can break the blind in case of an emergency.

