6.2. Assessments

The Adult ADHD Investigator Symptom Rating Scale (AISRS)

The AISRS is an 18-item, clinician-administered, semi-structured interview methodology developed to evaluate treatment responses (*Spencer et al. 2010*). The measure contains prompts and stem questions designed to capture the Diagnostic and Statistical Manual of Mental Disorders (DSM) symptoms of the disorder ADHD as they present in adulthood. Based on the responses from the patient, the administering clinician rates the symptom

severity as 0= none, 1= mild, 2= moderate, or 3= severe. The scale has been used and validated many times in a variety of clinical drug trials (*Adler & Gorny, 2015; Adler, Zimmerman, Starr, Silber, Palumbo, Orman & Spencer 2011 Goodman et al., 2017; Spencer et al., 2010*).

The Adult ADHD Self-Report Scale (ASRS)

The Adult ADHD Self-Report Scale (ASRS) Symptom Checklist is a self-report that presents the 18 DSM ADHD symptoms in adult context and is rated on a frequency basis. It was developed by the World Health Organization (WHO) work group on adult ADHD, and comprises an 18-item Symptom Checklist that corresponds to the 18 symptoms found in the DSM and a six-item screener of which the items were extracted from the symptom checklist) to help identify adults at risk of ADHD(Kessler et al., 2005;Ustun et al., 2017). The Screener and the Symptom Checklist use a 5-point Likert-type scale to rate ADHD symptoms (0 = never, 1 = rarely, 2 = sometimes, 3 = often, and 4 = very often). Depending on the question, "sometimes," "often," or "very often" suggest clinical impairment for that specific item. The ASRS v1.1 Symptom Checklist is designed to provide clinicians with an inventory of adult ADHD symptoms as the first part of a diagnostic evaluation or to be used in monitoring treatment response (Adler, Shaw, & Alperin, 2015; Adler et al., 2006). The ASRS has been expanded to include additional symptoms intended to assess executive function deficits (EFDs; nine items) and emotional dyscontrol (EC; four items). EFDs are deficiencies of high order cognitive processes, such as self-control, selfregulation, and ability to prioritize and to plan multiple tasks. EC includes symptoms of mood lability, irritability, and emotional overreactivity.

Time Sensitive Adult ADHD Symptom Scale (TASS)

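### A significant effect of week shows only within-patient change from the end of the placebo lead-in; the plan should not read it as the drug effect

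*Combined protocol and SAP*

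**What the plan says.** The rule of inference in 6.4.3.1 is: "For our design, a significant effect of week assesses the significance of the drug effect". It is repeated in 5.1, 6.4.1 and 6.4.4. The regression has one named predictor, the outcome being modelled "with weeks in trial after the end of the single-blind placebo lead-in as the independent variable". No treatment or phase term is mentioned.

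On the design, 5.1 says that after the lead-in "all patients will receive four weeks of Mydayis (12.5mg-37.5mg/day), with treatment order fixed", and 6.1.3 says "There is no plan for an assignment/randomization method after screening is complete". The hypothesis in 4.1 is that "after Mydayis treatment (from end of single-blind placebo lead-in) there will be significant improvement in" the listed outcomes, with AISRS total as the primary effect.

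On blinding, 6.1.4 says of patients: "The subject will not know when they are on placebo or when they start the Mydayis treatment". Of staff it says: "The research staff, including study doctor, will know if the patient is receiving Mydayis or placebo". Section 6.2 describes the leading scale: "The AISRS is an 18-item, clinician-administered, semi-structured interview methodology developed to evaluate treatment responses".

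The primary outcome is given in two ways. Sections 5.1 and 6.4.4 name AISRS total. The Synopsis (Primary Outcome Variables) and 6.4.1 name correlations between TASS and AISRS ratings.

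**The concern.** After the switch to Mydayis, week, drug exposure, dose titration and the number of repeated ratings all advance together, in every patient. One time coefficient from one sequence cannot divide the change among them. The hypothesis in 4.1 names the contrast that the data can answer, which is change from the end of the lead-in. The sentence in 6.4.3.1 goes further and attributes that change to the drug.

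This is the interpretation rule for the primary analysis of a study labelled Phase III, whose stated purpose includes extending the evidence for efficacy. Followed as written, it would turn any significant improvement from a non-drug source into a reported effect of Mydayis. No section available limits the conclusion to within-patient change.

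**Working it through.** **1. The plan's own figure.** Inputs from 6.4.2: 32 evaluable patients, Cohen's d 0.6, two-sided 0.05, and a baseline-to-endpoint difference. For a paired t-test the noncentrality is d·√n = 0.6 × √32 = 3.39 on 31 degrees of freedom, and power is 90.8%. The stated 90% or more is reproduced, and 32 is the smallest n that reaches it. The figure is correct for within-patient change. It is not power for drug against placebo: the same 32 patients split 16 and 16 would have 37.6% power at d = 0.6 (two-sample t).

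**2. What the 0.05 level protects against.** Assume that the drug does nothing and that AISRS changes for other reasons by dz, in SD units of the change. The documents give no such figure, so the range is illustrative. With noncentrality dz·√32:

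| Assumed non-drug change (dz) | Noncentrality | Significant |
|---|---|---|
| 0 | 0 | 5.0% |
| 0.2 | 1.13 | 19.5% |
| 0.5 | 2.83 | 78.2% |

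To express this in AISRS points, assume a between-patient SD of 8 and a correlation r between visits. The SD of change is 8 × √(2(1 − r)), which is 8.0 at r = 0.5 and 6.2 at r = 0.7. A dz of 0.2 is then 1.6 or 1.2 points, and 0.5 is 4.0 or 3.1 points, on a scale that runs to 18 × 3 = 54.

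**3. The regression itself.** The paired test in step 2 is suggested by the power statement. The analysis section names a regression on week, with no patient effect or covariance structure. Rejection rates with no change at all, simulated for 32 patients at weeks 0 to 4:

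| Within-patient correlation (assumed) | Week-only regression | Week plus a simple patient effect |
|---|---|---|
| Equal, 0.5 to 0.7 | about 0.1% to 0.7% | about 5% |
| Decaying, AR(1) 0.5 to 0.8 | about 3% to 8% | about 14% to 19% |

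The documents do not give the correlation, so the actual error rate of the regression cannot be stated. Under none of these settings does the test become a test of the drug.

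**4. Removal of placebo responders.** Patients whose AISRS falls by 30% or more in the lead-in are discontinued and left out of the analysis. If the end-of-lead-in score (Visit 3 in the schedule) is part of that rule, patients with a low score there are removed, and the rest tend to fall afterwards. Assume mean 38, SD 8, an inert drug, a placebo fall of 0 to 4 points and equal correlation of 0.5 to 0.7. The spurious improvement is then about 0.2 to 0.8 points where removal stays within the plan's 10%, and the paired test's type I error is 5.3% to 9.2%. If the rule uses only Visits 1 and 2, the bias is about 0 under equal correlation and about 0.1 to 0.5 points under AR(1) of 0.5 to 0.8.

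The window is not clear. Section 6.3 gives Visit 1 to Visit 2, while 6.3.5 and 6.4.3.1 refer to the lead-in as a whole. In 6.3 the visit numbers are also shifted: the part headed Week 1, Visit 2 lists its procedures under Visit 1, and the part headed Week 2, Visit 3 lists them under Visit 2.

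**The case against.** The best defence is that this is an openly single-arm study with safeguards. Patients do not know when Mydayis starts, the lead-in absorbs early placebo response, and responders are removed. Section 4.1 states the reference point, and the sample size is computed for baseline-to-endpoint change. All of that is true. It reduces expectancy and early drift, and it leaves the fault in the attribution sentence and not in the choice of design. It does not supply a concurrent control. The word randomized in the Synopsis, 5.3, 5.3.1 and 6.4.3.4 does not supply one either, since only one sequence is described and 6.1.3 plans no allocation.

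A reader might infer more than the documents support:

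- **The AISRS rater is certainly unblinded.** Section 6.1.4 makes this likely, but no available section names the rater, and Appendix 13 (schedule of events and providers) is listed without being shown. The point does not extend to the self-rated scales or the electronically scored WebNeuro tests.
- **The regression has a known faulty error rate, or a patient effect would restore 5%.** Both depend on the correlation structure. The plan names a framework and never says that records are treated as independent, and Appendix 17 (Statistical-Analysis-Plan) is not shown.
- **Responder removal matters only if the Visit 3 score enters the rule, or it explains any improvement seen.** The first holds only under equal correlation. The second does not fit the usually small size of the bias.
- **Comparing drug-phase with lead-in change would repair the design.** Such a contrast assumes that lead-in drift continues. Its SE is about √3 = 1.73 times that of simple change, so power at a drug-minus-placebo effect of 0.6 is 48%. Fixed order and rater knowledge would remain. I do not ask for it.

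**Conclusion.** The point holds for the attribution. As designed, a significant effect of week shows that patients changed after the end of the placebo lead-in; it does not by itself show that the drug caused the change. This follows from the fixed sequence, the absence of randomization and the single predictor, and rests on no numerical assumption. The rater point is an added and conditional reason for caution about the AISRS.

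The size cannot be fixed from the documents. The 20% and 78% rest on assumed drifts of 0.2 and 0.5 SD of change in a paired test with an inert drug. They show what the 0.05 level does not cover and do not predict this trial. Nothing here implies that Mydayis lacks effect, that a single-arm study is illegitimate, or that the sample size is wrong for the change it tests. The sentence must be corrected because it governs how the main result will be reported.

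**What to change.** 1. In 5.1, 6.4.1, 6.4.3.1 and 6.4.4, replace the sentence with: *a significant effect of week shows within-patient change from the end of the placebo lead-in and does not by itself establish a drug effect.* Report the result in those words.
2. Reconcile the primary outcome: TASS-AISRS correlations in the Synopsis and 6.4.1, against AISRS total in 5.1 and 6.4.4. A correlation contains no effect of week, so the rule of inference has no object under the first version.
3. Separate minor points: describe the analysed set as excluding placebo responders (modified ITT); align the three populations in 6.4.3.4, which are defined by randomization, with 6.1.3; and have the sponsor reconcile the responder window in 6.3 with 6.3.5 and 6.4.3.1, taking account of the shifted visit numbers in 6.3.

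The cost is one sentence in four places, one decision on the primary outcome and some definitions. No new data, patients or visits are needed. What is given up is the claim that the primary test by itself demonstrates efficacy, which the design cannot support.
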